1. STUDY SYNOPSIS

Study Phase: Exploratory (Phase 0/I)

Investigational Product:[177Lu]Lu-TEFAPI-06

Indication: fibroblast activation protein (FAP)-high expressing metastatic solid tumors

Methodology: Open-label, single-center, single-arm study

Sample Size: 5 participants

Intervention:Single intravenous injection of approx. 20 MBq/kg [177Lu]Lu-TEFAPI-06.

2. INTRODUCTION AND RATIONALE

FAP is highly expressed in the cancer-associated fibroblasts (CAFs) of the tumor microenvironment in various solid tumors, making it a promising target for radionuclide therapy. [177Lu]Lu-TEFAPI-06 is a novel radiopharmaceutical designed to target FAP. This study is initiated to evaluate its safety profile, biodistribution characteristics, and preliminary therapeutic potential in humans.

3. STUDY OBJECTIVES

3.1 Primary Objectives

1. To evaluate the safety and tolerability of [177Lu]Lu-TEFAPI-06 in patients with metastatic solid tumors.
2. To determine the biodistribution and calculate the radiation absorbed dose in normal organs and tumor lesions.

3.2 Secondary Objective

1. To preliminarily assess the therapeutic response of [177Lu]Lu-TEFAPI-06 in patients with FAP-high expressing tumors.

4. STUDY DESIGN

This is a prospective, single-center, open-label, exploratory clinical trial.

5 eligible patients will receive a single dose of the investigational drug.

Patients will undergo serial whole-body imaging to assess biodistribution and will be followed up for 1 month to assess safety and efficacy.

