6. TREATMENT PLAN

Drug:[177Lu]Lu-TEFAPI-06

Route of Administration: Intravenous (IV) injection.

Dosage: A single dose of approximately 20 MBq/kg.

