7. STUDY ASSESSMENTS AND PROCEDURES

7.1 Imaging Schedule

Following the injection of [177Lu]Lu-TEFAPI-06, whole-body planar imaging and SPECT/CT tomography will be performed at the following time points: 0.5 hours, 2 hours, 24 hours, 48 hours, 72 hours, and 120 hours post-injection.

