7.3 Safety Assessment

Vital signs and physical examination.

Laboratory tests: Complete blood count (CBC), Urinalysis, Liver function tests (LFTs), Renal function tests.

12-lead Electrocardiogram (ECG).

Adverse Event (AE) monitoring throughout the study.

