8. STATISTICAL ANALYSIS PLAN (SAP)

8.1 General Considerations

This is a small-sample exploratory study (N=5). The statistical analysis will be primarily descriptive. No formal sample size calculation based on power analysis was performed due to the pilot nature of the study.

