8.3 Biodistribution and Dosimetry Analysis

Data Processing:Regions of Interest (ROIs) will be drawn on whole-body SPECT/CT images for source organs (heart, lung, liver, kidney, spleen, brain) and tumor lesions.

Calculations:

1. Radioactive counts in ROIs will be converted to activity using system calibration factors.

2. Time-Activity Curves (TACs) will be generated for each organ.

3. Cumulative activity (residence time) will be calculated by integrating the TACs (using mono-exponential or bi-exponential fitting as appropriate).

4. **Software:**OLINDA/EXM software will be used to calculate the mean

absorbed dose (mGy/MBq) for organs and the effective dose (mSv/MBq) for the whole body.

Statistical Output: Mean and Standard Deviation (SD) of absorbed doses per organ will be reported.

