8.5 Safety Analysis

Adverse Events (AEs): All AEs will be coded and graded according to CTCAE v5.0 (Common Terminology Criteria for Adverse Events).

Tabulation: The number and percentage of patients experiencing AEs will be summarized by system organ class and severity grade.

Laboratory Data: Descriptive statistics will be used to summarize changes in hematology and chemistry values from baseline to post-treatment. Particular attention will be given to renal toxicity and myelosuppression (Grade 3/4 toxicity).

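### Nothing in the plan requires a pause or review between the 5 participants, even after a serious adverse event or a Grade 3/4 renal or haematological toxicity

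*Combined protocol and SAP*

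**What the plan says.** Section 2 introduces the agent in these terms: "177Lu]Lu-TEFAPI-06 is a novel radiopharmaceutical designed to target FAP". It gives the purpose as evaluating safety, biodistribution and early therapeutic potential in humans. Section 3.1 makes safety and absorbed dose the primary objectives. Section 4 states that "5 eligible patients will receive a single dose of the investigational drug", and section 6 sets the amount: "A single dose of approximately 20 MBq/kg". There is no escalation step.

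Each participant is imaged at "0.5 hours, 2 hours, 24 hours, 48 hours, 72 hours, and 120 hours post-injection" (section 7.1) and followed for 1 month (section 4). Section 7.3 lists "Laboratory tests: Complete blood count (CBC), Urinalysis, Liver function tests (LFTs), Renal function tests" but gives no post-injection times for them. It also calls for adverse event monitoring throughout.

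On use of the data, section 8.3 says "Mean and Standard Deviation (SD) of absorbed doses per organ will be reported". Section 8.5 says "Particular attention will be given to renal toxicity and myelosuppression (Grade 3/4 toxicity", within a descriptive summary. Section 9 makes the investigator responsible for safety monitoring and sends serious adverse events to the Ethics Committee within 24 hours. None of these sections links a result in one participant to the injection of the next.

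**The concern.** Each participant gets one injection, so what the trial learns about toxicity or organ dose can protect only those not yet injected. A single fixed dose level removes the review points that an escalation design would supply. As the plan stands, a further injection could follow a Grade 3/4 renal or haematological toxicity, or come before any participant's organ doses have been calculated, without any deviation.

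The existing safeguards act elsewhere. The exclusions in section 5.2 screen baseline organ function and blood counts. The serious-event report is a notification. A Grade 3/4 laboratory value need not be a serious adverse event, and a high organ dose is not an adverse event at all.

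**Working it through.** **Step 1: document check.** Each safety provision is set against its effect on the next injection.

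| Provision | Section | Effect on the next injection |
|---|---|---|
| Exclusion of organ dysfunction and low counts | 5.2 | None; baseline only |
| Adverse event monitoring, laboratory tests, ECG | 7.3 | None stated; no laboratory times, no action threshold |
| Organ dosimetry | 8.3 | None stated; output is a group mean and SD |
| Grade 3/4 renal and marrow toxicity | 8.5 | None stated; summarised |
| Serious-event report, investigator's duty | 9 | Permits a pause; requires none |

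The synopsis and sections 2 to 10 contain no dosing interval, sentinel participant, interim review, organ-dose limit, or hold or stopping rule.

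**Step 2: timing.** The last scan is at 120 h, which is 5 days. Four gaps of 5 days give at least 20 days from first to last injection. Allowing an assumed 2 days or so for processing, weekly injections fall on days 0, 7, 14, 21 and 28.

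**Step 3: illustration, for toxicity events only.** The plan has no figure to reproduce. Section 8.1 says "No formal sample size calculation based on power analysis was performed due to the pilot nature of the study", and no event rate or organ dose is given. From the plan: 5 participants, one injection each. Assumed: p, the probability per participant of an event that triggers a hold; k, the number of weeks after injection until the event is known; weekly injections; every hold permanent. The comparator is all 5 injected on day 0, giving 5 injected and 5p expected events.

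- P(injection j is given) = (1 − p)^max(0, j − k)
- E[N] = sum of these over j = 1 to 5
- Expected events = p × E[N]
- P(fewer than 5 injected) = 1 − (1 − p)^max(0, 5 − k)

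At p = 0.20 and k = 1: E[N] = 1 + 0.8 + 0.64 + 0.512 + 0.4096 = 3.36; expected events = 0.20 × 3.36 = 0.67; P(fewer than 5) = 1 − 0.8^4 = 0.59.

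| Event known (p = 0.20) | Expected injected | Expected events (comparator 1.00) | P(fewer than 5 injected) |
|---|---|---|---|
| within 7 days | 3.36 | 0.67 | 59% |
| within 14 days | 3.95 | 0.79 | 49% |
| within 21 days | 4.44 | 0.89 | 36% |
| within 28 days | 4.80 | 0.96 | 20% |
| later | 5.00 | 1.00 | 0% |

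If half the events are known by day 7 and the rest by day 14, E[N] = 1 + 0.9 + 0.72 + 0.576 + 0.461 = 3.66, with 0.73 expected events and a 54% chance of fewer than 5 injected.

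**Step 4: range over p.** From k = 1 to detection after day 28, expected events run from 0.41 to 0.50 at p = 0.10 (comparator 0.50) and from 0.83 to 1.50 at p = 0.30 (comparator 1.50).

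**The case against.** The strongest reply is that the modelled gain has no firm footing in this trial. The comparator is extreme: this is one centre, with individual PET/CT screening and six imaging sessions per participant, and nothing suggests that 5 simultaneous injections are planned. If accrual is already staggered and the investigator pauses when something happens, a written rule may avert no events. The most favourable row needs every event to be known within 7 days, which the documents do not support; at 28 days the gain is 1.00 − 0.96 = 0.04 events. The model also treats holds as permanent, whereas the proposed hold is reversible. Finally, a dosimetry review with no dose threshold ends in the same discretion the investigator has now. All of this stands. It limits the claimed benefit and means that the dosimetry review makes the look certain, not the action.

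It does not supply the missing requirement. The investigator may pause, but nothing obliges a pause, a review or a record of either. The dosimetry look also does not depend on how early toxicity appears, because the images through 120 h are already scheduled.

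Three stronger readings go too far. A reader might infer that all 5 will be injected together; the plan permits this but does not state it. A reader might infer a first-in-human trial; the text says novel and speaks of evaluation in humans, but makes no such statement. A reader might infer that safety oversight is absent; sections 5.2, 7.3 and 9 show otherwise.

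**Conclusion.** The point holds as a gap in required conduct: no pause or review between participants is mandated, even after a serious adverse event or a Grade 3/4 renal or haematological toxicity. That conclusion rests on the text alone and needs no assumed rate.

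Its size cannot be established from the documents. At p = 0.20, the 0.67 against 1.00 expected events is an upper bound on the benefit, conditional on concurrent dosing as comparator, permanent holds and detection within 7 days. The gain shrinks to 0.04 events if toxicity becomes known only at 28 days. It can be nil if toxicity appears later, or if accrual is already staggered with ad hoc pausing. A reader should not take one third fewer events as the expected effect of the change. The case for amending is that the change is cheap and the data are mostly being collected anyway, not that a known number of events would be prevented.

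**What to change.** **Section 9.** Hold further injections after any serious adverse event not clearly unrelated to the drug, or any Grade 3/4 renal or haematological toxicity in any participant, until a decision to continue is documented.

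**Section 4.** Inject one participant at a time. Before each next injection, the investigator documents a review of the previous participant's dosimetry through 120 h and of all safety data available, and records the decision to proceed or hold. The safety data should include a blood count and renal function test at about 120 h, which section 7.3 would need to schedule.

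An organ-dose level that triggers a hold is for the sponsor to set and is optional.

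**Cost.** A short amendment; possibly one extra blood draw; and up to about 4 weeks of added dosing time (last injection on day 28 rather than day 0), plus the length of any hold. If a hold becomes permanent, the organ-dose mean and SD rest on fewer than 5 participants; the last column of the p = 0.20 table gives the chance if every hold were permanent. No power calculation is lost, because the plan has none. Waiting out each 1-month follow-up would take about 4 months from first to last injection; that is a separate trade-off and not part of this change.

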5. STUDY POPULATION

5.1 Inclusion Criteria

1. Diagnosed with metastatic solid tumors via pathology.
2. Confirmed high FAP expression in tumor lesions via [18F]-FAPI PET/CT screening (Tumor uptake significantly higher than background).
3. Expected survival time > 3 months.
4. Voluntarily signed the informed consent form.

5.2 Exclusion Criteria

1. Pregnancy or lactation.
2. Severe hepatic or renal dysfunction (e.g., Creatinine > 1.5x ULN; ALT/AST > 3x ULN).
3. Severe hematological suppression (e.g., WBC < 3.0×10⁹/L, Platelets < 75×10⁹/L).
4. Known severe allergy to the drug or its components.

5. Any other condition that the investigator deems unsuitable for participation.

6. TREATMENT PLAN

Drug:[177Lu]Lu-TEFAPI-06

Route of Administration: Intravenous (IV) injection.

Dosage: A single dose of approximately 20 MBq/kg.

7. STUDY ASSESSMENTS AND PROCEDURES

7.1 Imaging Schedule

Following the injection of [177Lu]Lu-TEFAPI-06, whole-body planar imaging and SPECT/CT tomography will be performed at the following time points: 0.5 hours, 2 hours, 24 hours, 48 hours, 72 hours, and 120 hours post-injection.

7.2 Efficacy Assessment (Follow-up)

Timeline: Baseline (pre-treatment) and 1 month post-treatment.

Modality: [18F]-FAPI PET/CT.

Biological Markers: Tumor-specific serum markers will be measured at baseline and follow-up.

7.3 Safety Assessment

Vital signs and physical examination.

Laboratory tests: Complete blood count (CBC), Urinalysis, Liver function tests (LFTs), Renal function tests.

12-lead Electrocardiogram (ECG).

Adverse Event (AE) monitoring throughout the study.

8. STATISTICAL ANALYSIS PLAN (SAP)

8.1 General Considerations

This is a small-sample exploratory study (N=5). The statistical analysis will be primarily descriptive. No formal sample size calculation based on power analysis was performed due to the pilot nature of the study.

8.2 Analysis Sets

Full Analysis Set (FAS):All participants who received the study drug and have at least one post-baseline efficacy evaluation.

Safety Set (SS):All participants who received the study drug.

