8.4 Efficacy Analysis

Primary Endpoint (Imaging): Comparison of Standardized Uptake Values (SUV_{max} and SUV_{mean}) of the primary tumor and representative metastatic lesions between baseline and 1-month post-treatment [18F]-FAPI PET/CT scans.

Background Reference: Mean SUV of normal liver tissue.

Secondary Endpoint (Biomarkers): Comparison of serum tumor marker levels pre- and post-treatment.

Statistical Test: Continuous variables (SUV, biomarker levels) will be tested for significant changes using the Paired t-test (if normally distributed) or Wilcoxon signed-rank test (if non-normally distributed).

A P-value < 0.05 will be considered statistically significant.

Data will be presented as Mean \pm SD or Median (Range).

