8.6 Handling of Missing Data

Given the small sample size, missing data will not be imputed. Analyses will be performed on observed data only.

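### Does tying the full analysis set to a 1-month evaluation hide treated patients who deteriorate?

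*Combined protocol and SAP*

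**What the plan says.** Section 8.2 (Analysis Sets) gives two sets. The Safety Set is everyone dosed. The FAS is "All participants who received the study drug and have at least one post-baseline efficacy evaluation".

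Section 7.2 sets the efficacy timetable as "Timeline: Baseline (pre-treatment) and 1 month post-treatment". For blood markers it says "Tumor-specific serum markers will be measured at baseline and follow-up", and the only follow-up that section names is 1 month. Section 4 says patients "will be followed up for 1 month to assess safety and efficacy". It assigns the serial whole-body imaging (0.5 to 120 hours in section 7.1) to biodistribution, so those scans give no earlier route into the FAS.

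Section 8.4 compares SUVmax and SUVmean "between baseline and 1-month post-treatment [18F]-FAPI PET/CT scans", and compares markers before and after treatment, by paired t-test or Wilcoxon signed-rank test. It adds that "A P-value < 0.05 will be considered statistically significant". It names no analysis set and defines no responder rate.

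Section 8.6 states that "missing data will not be imputed. Analyses will be performed on observed data only". For safety, section 8.5 says "The number and percentage of patients experiencing AEs will be summarized by system organ class and severity grade".

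**The concern.** An FAS normally stays close to everyone treated. Here membership depends on reaching the single planned efficacy visit, because the condition of at least one evaluation can be met on no earlier scheduled date. A patient who dies, or becomes too ill to attend, before 1 month would leave the efficacy population because of the outcome.

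There is no control arm to show such selection, and each patient is 20% of those treated. Section 8.4 calls SUV the primary imaging endpoint of the efficacy analysis and attaches a significance threshold, so a reader might take a fall in uptake among the survivors as more than description. The safety tables would record the death or serious event, but the plan does not link it to the missing efficacy value or ask for the reason. The safety and dosimetry objectives, which are primary in section 3.1, are not touched. Response is the secondary objective in section 3.2.

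**Working it through.** **Inputs.** N = 5, with no power calculation (sections 4 and 8.1). One efficacy visit, at 1 month (7.2). Paired continuous comparisons (8.4). Observed data only (8.6). The documents give no loss rate, no expected change and no SD, so there is no stated figure to reproduce. Loss risks below are assumptions.

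**1. Does the FAS definition change any planned result?** Take a treated patient with baseline values and consider what exists at 1 month.

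| 1-month data | In FAS as written | In an all-treated set | SUV pair | Marker pair |
|---|---|---|---|---|
| Scan and marker | yes | yes | yes | yes |
| Scan only | yes | yes | yes | no |
| Marker only | yes | yes | no | yes |
| Neither | no | yes | no | no |

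The two definitions differ only in the last row, where the patient forms no pair under either. Every mean, median and test in section 8.4 is therefore identical. The third row shows that FAS membership does not even secure an SUV pair. The exclusion comes from the observed-data rule, not from the definition of the set.

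**2. How likely is a loss?** With independent per-patient risk d, the chance of at least one loss is 1 − (1 − d)^5:

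- d = 5%: 1 − 0.95^5 = 22.6%
- d = 10%: 1 − 0.90^5 = 41.0%
- d = 20%: 1 − 0.80^5 = 67.2%

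These count a loss for any reason. Only losses through deterioration bias the result in the way feared. Entry requires expected survival above 3 months (section 5.1) against 1 month of follow-up, which makes early death less likely but does not rule out a patient too unwell to scan.

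**3. How far could a planned mean move?** If k of 5 are lost, then

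mean over 5 = mean of those seen + (k/5) × (mean of those lost − mean of those seen).

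One loss moves the mean by 0.2 of the gap, and two by 0.4. The documents give no value for the gap. For scale, the 95% interval half-width for a mean change is t(0.975, n−1)/√n in SD units:

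- n = 5: 2.776/2.236 = 1.24 SD
- n = 4: 3.182/2 = 1.59 SD
- n = 3: 4.303/1.732 = 2.48 SD

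For the shift to equal the half-width, one lost patient would have to differ from the rest by 1.59/0.2 = 7.95 SD, and two by an average of 2.48/0.4 = 6.2 SD. Any bias is likely to be small beside the imprecision already present.

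**4. Do losses make significance easier to reach?** The smallest two-sided exact Wilcoxon P is 2/2^n: 0.0625 at n = 5, 0.125 at n = 4 and 0.25 at n = 3. The t critical value rises from 2.78 to 3.18 to 4.30. Both thresholds become harder to meet as patients are lost. That the Wilcoxon test cannot fall below 0.05 even with all 5 is a separate matter, which the choice of set does not affect.

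**5. What about proportions?** If every evaluated patient were lower at 1 month, one loss would give 4/4 = 100% (exact 95% interval 39.8 to 100%) against 4/5 = 80% (28.4 to 99.5%). Two losses would give 3/3 = 100% (29.2 to 100%) against 3/5 = 60% (14.7 to 94.7%). The contrast looks striking, but section 8.4 plans no such count. The figures describe an output that would first have to be added, in the extreme case where everyone seen is lower.

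**The case for a change.** The strongest case for a change is about visibility. Even if no test changes, the plan asks for neither the number evaluated nor the reason for a missing value, and section 8.4 leaves its analysis set unnamed. A report could in principle give a mean fall with a P-value and say nothing of a patient too ill to be scanned. Naming the set, labelling the comparisons as evaluated patients only and listing reasons would need no new data. One could go further and tabulate direction of change over all 5, with patients lost through deterioration counted as not lower.

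The facts in this stand: the number evaluated, the reasons and the set are not written down, and the survival criterion does not exclude every outcome-related loss. But a paired result on so few patients is hardly reported without its n. With one injection, progression cannot interrupt later doses, and no section removes a progressing patient from the 1-month scan. Adverse events are monitored throughout (section 7.3) and tabulated, and the Safety Set contains everyone dosed, so a death or serious event would be on record.

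The all-treated table is a different proposal. It would bring in a new endpoint, a rule for averaging lesions, a choice of one marker per patient and an assigned outcome for patients never measured. That last step sits badly beside section 8.6. The table would also count changes within scan or assay variation as lower, and it would not correct the mean change. It is a debatable addition, not the repair of an error.

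**Conclusion.** The reading of the text is right, but no change to the plan follows. FAS membership does hinge on the 1-month visit, and a patient lost through deterioration would be absent from the efficacy comparisons. Redefining the set would not bring that patient back, because sections 8.4 and 8.6 together use only observed pairs, so the gain in any planned result is nil.

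The bias in the mean change cannot be estimated from the documents. It is one fifth of an unknown gap for one loss and two fifths for two, against half-widths of 1.59 and 2.48 SD. It is zero if all 5 are evaluated. What remains is the number evaluated and the reasons for any gaps, detail that analysts of a five-patient, primarily descriptive study can be expected to supply when reporting.

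This rests on three assumptions: that section 8.4 is carried out as written, with paired continuous comparisons and no response rate; that losses in one month are few; and that the results are presented as the preliminary secondary evidence section 3.2 calls for. If a response proportion were later reported, the choice of denominator would begin to matter.

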8.3 Biodistribution and Dosimetry Analysis

Data Processing:Regions of Interest (ROIs) will be drawn on whole-body SPECT/CT images for source organs (heart, lung, liver, kidney, spleen, brain) and tumor lesions.

Calculations:

1. Radioactive counts in ROIs will be converted to activity using system calibration factors.

2. Time-Activity Curves (TACs) will be generated for each organ.

3. Cumulative activity (residence time) will be calculated by integrating the TACs (using mono-exponential or bi-exponential fitting as appropriate).

4. **Software:**OLINDA/EXM software will be used to calculate the mean

absorbed dose (mGy/MBq) for organs and the effective dose (mSv/MBq) for the whole body.

Statistical Output: Mean and Standard Deviation (SD) of absorbed doses per organ will be reported.

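### Section 8.3 plans a whole-body effective dose from six organs and tumours only, and does not say how remainder-of-body, bladder and red-marrow activity enter the calculation

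*Combined protocol and SAP*

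**What the plan says.** Objective 2 in section 3.1 is to determine biodistribution and to "calculate the radiation absorbed dose in normal organs and tumor lesions". Section 4 states: "Patients will undergo serial whole-body imaging to assess biodistribution". Section 7.1 schedules six imaging times up to 120 h: "whole-body planar imaging and SPECT/CT tomography will be performed at the following time points: 0.5 hours, 2 hours, 24 hours", then three later ones.

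Section 8.3 turns the images into doses. Regions "will be drawn on whole-body SPECT/CT images for source organs", and the full list reads "source organs (heart, lung, liver, kidney, spleen, brain) and tumor lesions". Then "Time-Activity Curves (TACs) will be generated for each organ", the curves are integrated using one- or two-exponential fits, and OLINDA/EXM gives the "absorbed dose (mGy/MBq) for organs and the effective dose (mSv/MBq) for the whole body". The output line is narrower: "Mean and Standard Deviation (SD) of absorbed doses per organ will be reported".

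The list carries no wording that leaves it open to further regions. No section mentions a whole-body or remainder curve, bladder contents, a voiding assumption, or a blood or marrow source. The laboratory tests in section 7.3 are safety tests; none counts radioactivity in blood or urine. Section 8.5 singles out kidney toxicity and myelosuppression. Kidney has a source region; marrow has none.

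**The concern.** Effective dose is a weighted sum over the whole body, so it needs an account of decays throughout the body. Section 8.3 describes the calibration, curve fitting and software, but gives an account only for six organs and tumours. Two analysts could follow it faithfully, enter different things for the rest of the body, and report different effective doses. The error would be systematic across all five patients, so the planned mean and SD would not reveal it. The figure could not be reproduced or fairly compared with another agent.

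Marrow raises a related point. It is the tissue behind one of the two toxicities named in 8.5, and a marrow value obtained without a marrow or blood term leaves out marrow's own activity.

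**Working it through.** The plan states no dose, residence time or excretion figure, so there is nothing of its own to reproduce. What can be checked is direction, and sensitivity under stated assumptions.

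**1. Direction if only the listed regions are entered.** Dose to a target is D(target) = Σ Ã(source) × S(target←source), where Ã is cumulated activity. Effective dose is E = Σ w(target) × D(target). Every Ã, S and w is zero or positive, so dropping sources cannot raise E, and dropping sources that irradiate weighted tissues lowers it. A numerical check agreed: in 20,000 random non-negative sets, removing three of nine sources never raised E. For marrow, the self-dose term is zero by construction and only cross-dose from entered sources remains.

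**2. Direction if all unlisted decays go to the remainder with no excretion.** Activity that has left the body is counted as if it decayed there. E is then too high to the extent that the agent is excreted.

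**3. Sensitivity of the decays entered.** Assumptions, none from the document: lutetium-177 physical half-life 6.65 days (6.65 × 24 = 159.6 h); mono-exponential whole-body effective half-life T of 10 to 100 h; listed regions holding 20–60% of the decays in the body.

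- Listed regions only: 0.20 to 0.60 of the true decays are entered.
- No excretion: the total entered is 159.6 / ln 2 = 230.3 MBq·h per MBq injected. The true total is T / ln 2, so the ratio is 159.6 / T.

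| T (h) | True total (MBq·h/MBq) | No-excretion total ÷ true total |
|---|---|---|
| 10 | 14.4 | 16.0 |
| 30 | 43.3 | 5.3 |
| 60 | 86.6 | 2.7 |
| 100 | 144.3 | 1.6 |

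These are ratios of decays, not of effective dose or marrow dose.

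**4. A rough translation into effective dose, listed regions only.** Further assumptions: 70 kg body; listed organs of mass m = 4–5 kg holding a share f = 10–60% of decays and carrying W = 20–50% of the tissue weight; self-dose only; remainder spread evenly. Then E(listed) = W × f/m and E(full) = E(listed) + (1 − W) × (1 − f)/(70 − m).

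- m = 5, f = 0.1, W = 0.2: 0.0040 against 0.0040 + 0.8 × 0.9/65 = 0.0151, understated by 73%.
- m = 4, f = 0.6, W = 0.5: 0.0750 against 0.0750 + 0.5 × 0.4/66 = 0.0780, understated by 4%.

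The range runs from trivial to large, and nothing in the document narrows it.

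**5. How well the images could support a voiding model.** No scan falls between 2 and 24 h. The share of whole-body decays in that gap is exp(−2 ln 2/T) − exp(−24 ln 2/T): 0.68, 0.38, 0.22 and 0.14 at T = 10, 30, 60 and 100 h.

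**The case against.** The strongest reply is that 8.3 says where regions are drawn, not that nothing else is entered in the software. It refers to whole-body images and a whole-body dose, and a dosimetrist may add a remainder by habit. A reader might therefore infer from the list that effective dose will certainly be understated. The document does not support that: understatement holds only if the listed regions alone are entered, and the opposite error is possible. What stands is that the text taken literally gives too low a figure, and that habit does not settle the excretion assumption on which the result depends.

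A second reply is that little hangs on it. Effective dose is in no objective, and the output line in 8.3 covers absorbed doses per organ only. That is right and limits the weight of the point, but step 4 of 8.3 still plans the quantity.

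Third, marrow. A reader might infer that objective 2 fails without a marrow dose. The document does not itemise the normal organs or promise a marrow dose, and 8.5 assesses myelosuppression through blood counts and CTCAE grades, not dose. The heart region could also serve as a blood surrogate. What remains is that 8.3 does not say so, and any marrow value produced would have no stated basis.

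Finally, a voiding model fitted across the 2–24 h gap would be weakly supported. This also stands, and is a reason to report the uncertainty.

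**Conclusion.** The point holds as a gap in the specification that should be fixed. Entering only the listed regions makes effective dose too low and leaves any marrow value with cross-dose only; a remainder with no excretion makes effective dose too high. The plan does not choose between these or any third course.

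The size for this trial is unknown. The figures above rest on assumed half-lives, shares, masses and weights; they show sensitivity and do not set the importance of the point. In particular, the 16-fold ratio is the extreme of one branch and counts decays, so it should not be read as an error in dose.

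Nor does the point extend to the main dosimetry results: self-doses to the listed organs, kidney included, and to tumours are little affected. No decision in the plan depends on effective dose. Marrow dose matters through its relevance to the toxicity named in 8.5.

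**What to change.** Amend 8.3, using the images already scheduled:

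- **Bladder.** Add urinary bladder contents as a source, and bowel if visible, with a stated voiding model fitted to the whole-body curve. Report the uncertainty that comes from having no scan between 2 and 24 h.
- **Marrow.** Take red-marrow activity from a metastasis-free vertebral region, or from the heart blood-pool curve as a stated surrogate that assumes no specific marrow uptake.
- **Remainder.** At each time point, define it as measured whole-body activity minus the sources entered separately in OLINDA/EXM. Subtract tumour activity only if its contribution to normal-organ and effective dose is accounted for separately; otherwise keep it in the remainder, since subtracting it would drop those decays. State which is done.
- **Coverage.** State in 7.1 and 8.3 whether SPECT/CT itself covers the whole body. If not, measure whole-body activity on the planar scans, calibrated consistently with SPECT.
- **Reporting.** Give marrow dose alongside kidney dose.

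If these terms are not added, state that effective dose and marrow dose will not be reported.

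The cost is a few more regions per scan and an edit to the text, with no new scans or samples. Planar-to-SPECT calibration is needed only if SPECT/CT does not cover the whole body. Recording voiding times would help but is optional. The price in interpretation is an effective dose with openly wider uncertainty: under the half-lives assumed above, 14% to 68% of whole-body decays fall in the unscanned interval.
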